This is a 6-year, 5-site, randomized behavioral efficacy trial of 600 participants with the MetS. Trial coordination is conducted by a research coordinating unit (RCU) and an intervention coordinating unit (ICU), located within the Department of Preventive Medicine at Rush University Medical Center in Chicago. Patients with MetS who are motivated to manage it by changing their lifestyle, and do not have any medical contraindications or logistical barriers, are recruited serially from each of the 5 participating clinical centers over 4 waves of 6-month recruitment periods. Each site is expected to recruit 30 participants/wave, and 120 participants over all 4 waves, to achieve a total of 600 participants in the trial. Recruitment proceeds in 3 steps to confirm medical, behavioral, and logistical eligibility. Once a site has recruited 30 participants, they are randomized in a ratio of 1:1 to the Group-based or Self-Directed arm. Randomization is stratified by site in permuted blocks. Outcome evaluation is conducted at baseline, at the end of the intensive phase of the intervention at approximately 6 months, halfway through the maintenance period at approximately 15 months, and at the end of follow-up at approximately 24 months. **Figure 1** presents the trial design. **Figure 2** presents the timeline for the 6-year trial including the set-up, serial recruitment in 4 waves, intervention, and maintenance. This revised trial timeline reflects a 4-5 month suspension of in-person visits due to the Covid-19 pandemic.

[figure not shown]

Figure 1. Trial design

[figure not shown]

Figure 2. Trial timeline

EQUIPOISE AND BLINDING

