Component 2 (Run-In Period). A Run-In period was developed to identify those who are willing and able to engage in a selected set of activities required by the Group-Based program. This Run-In includes successful completion of the accelerometer protocol (wear accelerometer for 7 consecutive days, 10 hours/day), food and beverage logs (record all food and beverage intake over an entire day for a minimum of 3 weekdays and 1 weekend day), and completion of a worksheet that outlines a logistical plan for how to access vegetables and a location for physical activity (completed at home or during Visit B).

Component 3 (Visit B). The second in-person visit includes a 12-hour fasting blood draw, physical measures, confirmation that the Run-In protocol was completed successfully, and completion of baseline questionnaires. Visit B occurs within 1 month of randomization. At the conclusion of Visit B, prospective participants are asked about continued interest, informed of expected wait time until the start of the program, and entered into the recruitment waiting protocol where they are kept informed of likely dates of starting treatment in ongoing contacts every 2 weeks. If a prospective participant is ineligible based on metabolic syndrome criteria or needs medical clearance for trial participation, the research assistant will follow-up with a phone call.

Randomization

Randomization is conducted by the RCU in permuted blocks and stratified by site. Since 1 of the arms in the trial is a group-based treatment of 15 participants/group, randomization will occur when 30 prospective participants are confirmed to be eligible and interested. Treatment should begin immediately after randomization. Upon randomization, participants are informed of the arm to which they were randomized by a mailed letter, an email, and a follow-up phone call from the respective site interventionist.

As randomization progresses, key population descriptors are compared in the trial arms to ensure that randomization is successfully balancing arms on key baseline characteristics. If any key covariate, such as age, race, gender, employment status, weight, or MetS component, differs by treatment arm, additional stratification in the randomization scheme is considered.

INTERVENTIONS

Highly motivated participants are recruited to help determine the better and more cost-effective way to encourage sustained lifestyle change to reverse the MetS.

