Withdrawal from the Trial. This status applies to a participant who is no longer willing to participate in any part of the ELM trial, including group meetings, phone calls, or follow-up visits. However, the participant may allow the trial to use lab and medical data routinely collected by his/her provider.

Withdrawal of Consent. This status applies to a participant who no longer wishes to participate in the trial and declines use of data collected during routine visits with the provider. The status must be requested in writing by the participant and reported to the IRB.

Administrative Withdrawal. This status applies to a participant for whom it is no longer safe for the participant or for the trial staff to continue involvement in the trial. The ELM Safety Committee makes this determination in collaboration with the local site PI. This status terminates all further contact with the participant.

Deceased. This status is assigned once confirmed by the safety committee after review of the adverse event.

RETENTION

Retention has been excellent (90-100%) in the past clinical trials administered by the coordinating center at Rush. However, to assume a conservative approach, the sample size is calculated assuming a 20% loss to follow-up at 24 months. Key strategies to enhance retention include: (1) patient-centered recruitment emphasizing consideration of both the pros and cons of participation, from the participant’s perspective; (2) maintaining 2-3 alternative contacts for each participant at enrollment; (3) same staff member assesses outcomes and maintains regular contact with participant over time; (4) minimization of transportation burden by providing free parking and transportation vouchers; (5) reimbursement for assessment time; (6) reminders about appointments for scheduled intervention and follow-up visits; (7) birthday and holiday cards; (8) collaborative partnerships with providers in participating clinics to enhance their support for their patient’s participation; and (9) negotiating with potential drop-outs to encourage partial withdrawal rather than withdrawal of consent. To reduce

differential drop out, all staff are trained and re-trained to insure equipoise, enthusiasm for a conclusive answer to the question rather than a specific result, and timely response to participant inquiries.

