Consideration must be given to the fact that the proposed trial employs a “partially clustered” design where clustering is present in only 1 of the 2 arms. The Group-Based Program is delivered to participants in groups, or clusters, of approximately 15 participants. Connection and interactivity within each of these “experimentally-induced” clusters is a key component. The intraclass correlation coefficient (ICC) measures the extent to which participant responses are influenced by the cluster to which they belong. Since this clustering feature is present in only one of the two arms, its effect is muted. Results from our previous studies are consistent with those of others [13-14] indicating that the ICC could reasonably range from 0.01 to 0.20. We conservatively assume an ICC of 0.15 and adjust the total sample size required to achieve 85% power to 286 per arm or a total sample size of 572. We adjust upward to 300 participants/arm, a total sample size of 600 participants, 120 participants at each of 5 clinical sites, and 8 intervention clusters per site.

ANALYSIS PLAN

Analyses will be performed using an intent-to-treat approach that includes all patients as randomized, regardless of treatment dose. All analyses will use two-sided tests conducted at $\alpha=0.05$. Basic summary statistics will be based upon cluster-adjusted chi-square tests and t-tests. If a distribution is non-normal, cluster-adjusted

Wilcoxon rank sum tests will be used. Supplemental analyses will include mixed effects regression models to account for cluster effects and control for important covariates. The impact of missing data will be evaluated using sensitivity analyses. If data are missing at random, multiple imputation will be employed. If data are not missing at random, an appropriate statistical model will be employed (e.g. a pattern mixture model with sensitivity analyses).

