The primary hypothesis is achievement of a clinically significant MetS remission at 24 months in $\geq 40\%$ of the participants in the Group-Based program and $\leq 20\%$ of the participants in the Self-Directed program. Achieved rates will be observed, relative to these benchmarks, without statistical support. The primary statistical analysis will compare MetS remission at 24 months between the trial arms using a cluster-adjusted chi-square test. A secondary analysis will compare these rates using a mixed effects logistic regression model examining treatment over time (i.e., baseline through 24 months), a treatment*time interaction, and adjustments for age, gender, race/ethnicity, socioeconomic status, geographic site, BMI, number of co-morbidities, and number of MetS components. Random effects (e.g. random intercept, time, intervention cluster) will be included in the model only if they significantly improve model fit as determined by the likelihood ratio test.

Behavioral treatment targets will be compared by arm, without statistical support, as the proportion of participants achieving clinically significant goals (as presented in the hypothesized pathway in **Figure 3**), based upon the pre-determined benchmarks. Statistical support will be provided by a cluster-adjusted chi-square test. All other secondary and exploratory outcomes will be compared using the relevant cluster-adjusted t-test or chi square test. These comparisons will be conducted using data from post-intensive intervention, mid-maintenance, and end-of-treatment visits and trends over time will be examined. Supplementary analyses will use generalized linear mixed effects modeling, with a behavioral treatment target or weight as the outcome, treatment group as the primary predictor, random effects to account for time, site, and cluster, and selected covariates.

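### The secondary mixed model of MetS remission keeps the intervention-cluster effect only if a likelihood ratio test is significant, although the clustering is built into the design

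*Combined protocol and SAP*

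**What the plan says.** The Analysis Plan makes a cluster-adjusted chi-square test the primary comparison of 24-month remission. A secondary mixed effects logistic model covers baseline to 24 months, with a treatment-by-time interaction and covariates. For that model it adds: "Random effects (e.g. random intercept, time, intervention cluster) will be included in the model only if they significantly improve model fit". The criterion is the likelihood ratio test (LRT); neither its level nor its reference distribution is given.

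Three other statements bear on this:
- The Sample Size section treats the Group-Based groups as clusters produced by the intervention, cites evidence "indicating that the ICC could reasonably range from 0.01 to 0.20", and plans on 0.15.
- The opening of the Analysis Plan gives the purpose of the mixed models: "Supplemental analyses will include mixed effects regression models to account for cluster effects and control for important covariates".
- The supplementary models for behavioral targets and weight have "random effects to account for time, site, and cluster", with no significance condition.

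**The concern.** The plan treats clustering as certain when it sets the sample size and as optional when it fits this model. It also handles the same groups in two ways within the Analysis Plan.

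A non-significant LRT is weak evidence of no clustering when there are few groups and the ICC is small. If the term is dropped while clustering is real, Group-Based participants are analyzed as independent and the standard error of the arm effect is too small. The covariate-adjusted, longitudinal analysis of the primary endpoint could then disagree with the cluster-adjusted primary test for a purely procedural reason.

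The rule also names the participant random intercept. No harm is claimed there, because with repeated visits that term will usually be retained.

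**Working it through.** **The plan's own figures.** The plan gives no type I error for this model, but its sample size can be checked. For 40% against 20%, two-sided 0.05 and 85% power:

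n = [1.96·√(2·0.3·0.7) + 1.036·√(0.4·0.6 + 0.2·0.8)]² / 0.2² = 92.7, so 93 per arm. Allowing 20% loss, 93/0.8 = 116.25, so 117, as stated. With design effect 1 + 14·0.15 = 3.1, 92.7·3.1 = 287, close to the stated 286.

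**Inputs.**
- Trial Design: "Each site is expected to recruit 30 participants/wave, and 120 participants over all 4 waves". Randomization: "Since 1 of the arms in the trial is a group-based treatment of 15 participants/group". Five sites × 4 waves give 20 groups of 15.
- Sample Size: "120 participants at each of 5 clinical sites, and 8 intervention clusters per site". That would be 40 groups of 300/40 = 7.5. Both layouts were run.
- Retention: "the sample size is calculated assuming a 20% loss to follow-up at 24 months". Evaluable: 15·0.8 = 12 or 7.5·0.8 = 6 per group, and 300·0.8 = 240 Self-Directed participants.
- Assumed: a common remission rate of 30% (midpoint of 40% and 20%) and an LRT cut-off of 3.84.

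**What dropping the term costs.** With equal arms and group size m, the true variance of the arm difference exceeds the unadjusted one by (D + 1)/2, where D = 1 + (m − 1)·ICC. For m = 12:
- ICC 0.05: D = 1.55, ratio 1.275, effective critical value 1.96/√1.275 = 1.736, true error 8.3%.
- ICC 0.10: D = 2.10, ratio 1.55, critical value 1.574, error 11.5%.
- ICC 0.15: D = 2.65, ratio 1.825, critical value 1.451, error 14.7%.

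These are the errors if the term were always dropped. The rule drops it only sometimes, so simulation is needed.

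**Simulation under the null at 24 months.** Beta-binomial groups, independent controls, maximum likelihood ICC, LRT of zero ICC, then a z-test with or without the estimated design effect; 20,000 runs per ICC (Monte Carlo SE about 0.17 points per rate).

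| ICC | 20×12: dropped | Rule / always keep | 40×6: dropped | Rule / always keep |
|---|---|---|---|---|
| 0.02 | 92% | 6.0 / 5.3% | 94% | 5.4 / 4.8% |
| 0.05 | 71% | 7.2 / 5.8% | 82% | 5.8 / 5.1% |
| 0.10 | 32% | 7.0 / 6.1% | 48% | 6.4 / 5.6% |
| 0.15 | 11% | 6.8 / 6.4% | 20% | 6.1 / 5.6% |
| 0.20 | 3% | 6.8 / 6.7% | 6% | 5.8 / 5.7% |

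The largest excess is at ICC 0.05 with 20 groups. The rounded entries differ by 1.4; a repeat run gave 6.7 against 5.4%, or 1.3. Within Monte Carlo error the peak is about 1.3.

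**Sensitivity.**
- *Model.* A logistic-normal random-intercept model with a Wald test (20×12, rate 30%) gives an excess of 1.29 points at ICC 0.04, 1.26 at 0.05, 0.83 at 0.10 and 0.28 at 0.15. With 40 groups of 7 the peak is about 1.0.
- *LRT cut-off.* With the boundary-corrected 2.71 and 20 groups, the term is dropped in 62%, 23% and 7% at ICC 0.05, 0.10 and 0.15. The excess is 6.8 − 5.8 = 1.0, 6.7 − 6.1 = 0.6 and 6.6 − 6.4 = 0.2 points.
- *Reference distribution.* With t(19) on both sides, rule against always keep is 5.5 / 4.4%, 5.5 / 4.7% and 5.2 / 4.8%: an excess of 1.1, 0.8 and 0.4 points.
- *Repeated visits.* A normal approximation for the mean of three follow-up visits used 20 groups, an assumed within-person correlation of 0.3–0.7 and a constant group effect. The term is dropped in 36–61%, 4–18% and 0.4–4% at ICC 0.05, 0.10 and 0.15; the excess is 1.0–1.3, 0.2–0.6 and 0.0–0.2 points.

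**Trials where the term is dropped.** In these, the unadjusted test rejected a true null in about 9%, 12% and 18% at ICC 0.05, 0.10 and 0.15 (20 groups). The averages understate the error in a report from such a trial.

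**The case against.** The strongest reply is that little is at stake. The primary test is cluster-adjusted without condition, as are the basic secondary comparisons. The peak needs an ICC near 0.05 and 20 groups; at the planning ICC of 0.15 the excess is at most about half a point. All of this stands and sets the weight of the point. But the plan itself calls 0.15 conservative, so lower values, where the rule does most damage, are plausible.

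Second, part of the departure from 5% is not due to the rule. At ICC 0.15 with 20 groups, always keeping the term still gives 6.4% with a normal reference. This also stands, and is why only the difference between the columns is attributed to the rule. The remainder calls for a small-sample reference distribution, a separate matter.

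Third, the planned model was not fitted. It is longitudinal, and adjustment for site and other covariates could absorb some group variance. If the reported contrast were a within-person change and the group effect were the same at every visit, including baseline, the group effect would cancel and dropping the term would matter little. That condition does not fit change from baseline: groups form after randomization and every participant has MetS at entry. Cancellation could apply to changes between follow-up visits, and the plan does not say which contrast it will report. The harm described here concerns the arm difference at 24 months or averaged over follow-up.

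**Conclusion.** The concern holds. A significance test should not decide whether a design-induced cluster effect stays in the model, and the rule conflicts with the plan's stated purpose for its mixed models and with its own supplementary models.

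The effect is modest: up to about 1.3 points of added type I error near ICC 0.05 with 20 groups, about 0.8 at most with 40 groups of 6, and roughly 0 to 0.5 at ICC 0.15. It is confined to the secondary logistic model.

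The figures rest on an assumed 30% remission rate, 20% loss spread evenly over groups, an LRT at 0.05 and a model without covariates. The exact size in the planned model is therefore uncertain, but the direction is not. The change should be made; it does not bear on the primary conclusion.

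**What to change.** State in the Analysis Plan that the secondary logistic model always includes, by design and whatever the LRT shows, a random effect for intervention cluster in the Group-Based arm (no cluster variance in the Self-Directed arm) and a participant random intercept. Limit LRT selection to optional random time slopes.

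This costs one sentence and slight conservatism if clustering is absent: at ICC 0, always keeping the term gives a type I error of 4.4% with 20 groups and 4.7% with 40, using a normal reference.

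As a separate refinement, name a t or F reference with degrees of freedom based on the actual number of groups. This first requires reconciling the 20 groups implied by the Trial Design and Randomization sections with the 8 clusters per site in the Sample Size section. It costs more at ICC 0, where the type I error would be 3.3% with 20 groups or 4.0% with 40, but it addresses the inflation that remains at higher ICCs.

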Compare the Group-Based and Self-Directed arms on the behavioral risk factor targets of the treatment, and other secondary outcomes, at 6, 15, and 24 months.

Aim 2a: Compare the Group-Based and Self-Directed arms on the proportion of participants achieving clinically significant improvement in behavioral risk factor targets of treatment: (1) 2 cups of vegetables/day; (2) at least 150 minutes of moderate intensity physical activity/week; (3) either the maximum score, or an increase of ≥ 1 standard deviation of baseline distribution, on the 3-facet Mindfulness Questionnaire; and (4) a score of ≥ 4 on each of the four domains of the Self-Reported Habit Index (diet, physical activity, emotion control, and sensory awareness).

Aim 2b: Compare the Group-Based and Self-Directed arms on the secondary outcomes of: (1) $\geq 5\%$ loss of baseline weight; (2) kg of weight lost; (3) frequency of sugary beverage intake; (4) energy/vitality; (5) depressive symptoms; (6) social support for diet and exercise; (7) frequency of contacts with the health network; (8) perceived stress; (9) eating competence; (10) MetS components; (11) MetS severity; (12) Hemoglobin A1C; and (13) body mass index.

AIM 3.

Conduct a comprehensive health economic evaluation of the Group-Based and Self-Directed programs.

Aim 3a: Calculate the cost-effectiveness of the Group-Based relative to the Self-Directed programs. Cost-effectiveness is quantified using the Incremental Cost-Effectiveness Ratio and will reflect the cost of the programs in the two arms relative to their efficacy at promoting a sustained remission of the MetS.

Aim 3b: Model the projected clinical benefits and health care savings associated with dissemination of the Group-Based and Self-Directed programs.

Aim 3c: Compare the Group-Based and the Self-Directed programs on the number and dose of

medications, and health care utilization (primary care visits, specialty care visits, emergency room visits, hospital admissions) at 2 years.

EXPLORATORY AIMS

AIM 4.

Evaluate the consistency of impact and delivery across national sites.

Aim 4a: Explore the efficacy of the Group-Based and Self-Directed programs in subgroups defined by: geographic site, type of recruitment, age, gender, race/ethnicity, education, income, and number of MetS components.

Aim 4b: Explore the fidelity of delivery of the Group-Based and Self-Directed programs by geographic site.

TRIAL DESIGN

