The health economic evaluation features the incremental cost effectiveness ratio (ICER) for the 2 trial arms, where the $ICER = (C_1 - C_0)/(E_1 - E_0)$, and C is intervention cost, E is effectiveness at remission of MetS, subscript 1 denotes the Group-Based arm, and subscript 0 denotes Self-Directed arm. The ratio yields the cost differential for MetS remission in the 2 trial arms. In addition, the ICER will be calculated for each Quality-Adjusted Life Year (QALY) gained. The analysis will be conducted from the commercial payer, public payer, and societal perspectives. Sensitivity analyses will be conducted to account for the potential influence of plausible changes in cost assumptions.

The projected benefits of disseminating the Group-Based Program will be modeled by combining the observed rate of MetS remission in the trial with published national estimates of cardiometabolic disease risk and added health care costs associated with MetS. Projections will focus on the number of potential cases of type 2 diabetes, coronary heart disease, and stroke averted, and potential healthcare savings, in the overall adult population, Medicare population (65+), adults on Medicaid, and privately insured adults.

Exploratory analyses examine the efficacy to treatments within important population subgroups. These comparisons will be presented by forest plots. Intervention fidelity within each treatment arm is monitored on an ongoing basis by the Intervention Coordinating Unit, with remediation delivered promptly when problems are identified. Observed fidelity data will be compared to the clinically significant goal of at least 80% adherence to key components for the overall trial, and stratified by geographic site.

TRIAL ORGANIZATION

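### The dissemination projection (Aim 3b) takes a remission rate as its effect instead of the between-arm difference, so on its natural reading it credits the Group-Based program with remission that also occurs under Self-Directed

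*Combined protocol and SAP*

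**What the plan says.** The health economic part of the Analysis Plan has two components.

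- **ICER.** It is the cost difference divided by the effectiveness difference, where "subscript 1 denotes the Group-Based arm, and subscript 0 denotes Self-Directed arm". The effect is incremental. The sensitivity analyses named there are limited to cost: "Sensitivity analyses will be conducted to account for the potential influence of plausible changes in cost assumptions".
- **Dissemination model.** The next paragraph begins "The projected benefits of disseminating the Group-Based Program will be modeled" and gives the method as "combining the observed rate of MetS remission in the trial with published national estimates of cardiometabolic disease risk", together with the added health care costs of MetS. The outputs are cases of type 2 diabetes, coronary heart disease and stroke averted, and savings, "in the overall adult population, Medicare population (65+), adults on Medicaid, and privately insured adults".

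Aim 3b in the Specific Aims is wider. It is to "Model the projected clinical benefits and health care savings associated with dissemination of the Group-Based and Self-Directed programs". The Analysis Plan gives no method for a Self-Directed projection and does not say that a difference between two projections will be reported.

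On who was enrolled, Recruitment and Randomization says of the run-in that it serves to "identify those who are willing and able to engage in a selected set of activities required by the Group-Based program". Failing to complete it is an exclusion criterion, and the Interventions section describes the participants as highly motivated.

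**The concern.** A case averted is a causal quantity: it is the difference between what happens with the program and what would have happened under an alternative. A remission rate observed in one arm is not such a difference. The protocol's own hypothesis allows remission in up to 20% of the Self-Directed arm, so part of any Group-Based rate would be matched without that program.

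The plan writes an increment where it defines the ICER and a level one paragraph later. The two economic results could therefore rest on different effects from the same trial and point in different directions. If the arms did not differ, the ICER would have a zero denominator while the projection still showed cases averted and money saved. An analyst who used the gross rate would be following the plan as written.

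A separate, lesser matter is that the rate comes from a selected sample and is carried to national populations with no stated uptake, eligible share or sensitivity analysis on the effect.

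**Working it through.** **Inputs**

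- Group-Based remission p1 = 40% and Self-Directed remission p0 = 20%: Primary Aim 1 (stated as at least 40% and at most 20%).
- Two-sided alpha 0.05 (Analysis Plan) and power 85% (Sample Size).
- 20% loss to follow-up at 24 months: Retention.
- 86 million Americans with MetS: Background. Used only for scale.

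**Step 1. Are 40% and 20% the plan's working rates?** The Sample Size section gives 117 per group before clustering, without restating the rates. With pooled variance and no continuity correction:

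n = [1.96 × √(2 × 0.30 × 0.70) + 1.036 × √(0.40 × 0.60 + 0.20 × 0.80)]² / 0.20² = 92.7, rounded up to 93.

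Allowing for 20% loss: 93 / 0.8 = 116.25, rounded up to 117 per group, or 234 in total. This reproduces the stated figures, so the two rates are the plan's own.

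**Step 2. Gross against net projection.** For N people treated, the gross count is p1 × N and the net count is (p1 − p0) × N. Their ratio is p1 / (p1 − p0), which does not depend on N.

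| p1 | p0 | Gross per 1,000 | Net per 1,000 | Ratio |
|---|---|---|---|---|
| 40% | 10% | 400 | 300 | 1.33 |
| 40% | 15% | 400 | 250 | 1.60 |
| 40% | 20% | 400 | 200 | 2.00 |
| 40% | 30% | 400 | 100 | 4.00 |
| 20% | 20% | 200 | 0 | not defined |

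The ratio can be written 1 / (1 − p0/p1). If the hypothesis holds (p1 at least 40%, p0 at most 20%), p0/p1 is at most 0.5, so 2.0 is the largest factor compatible with it. If the arms turn out closer than hypothesized, the factor is larger, as the 40% and 30% row shows. The last row is the equal-arms case: nothing is gained over Self-Directed, yet the gross input gives 200 remissions per 1,000.

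**Step 3. Scale.** Assuming full uptake, which the protocol does not state, among the 86 million with MetS:

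- gross: 0.40 × 86 = 34.4 million remissions;
- net: 0.20 × 86 = 17.2 million.

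Half of the credited remissions would also occur under Self-Directed.

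**Step 4. The texts side by side.**

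| Place | Programs covered | Effect used |
|---|---|---|
| ICER, Analysis Plan | both | difference, E1 − E0 |
| Dissemination model, Analysis Plan | Group-Based only | an observed rate, arm not named |
| Aim 3b, Specific Aims | both | not stated |

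**The case against.** The strongest reply is that gross use is an inference. The phrase names neither an arm nor a contrast, and because Aim 3b covers both programs, the sponsor may intend two projections from which the difference can be read. This stands in part. A reader might infer that the plan commits to an attribution error; the documents do not show that. But the only sentence giving a method projects the Group-Based program alone, and two projections would settle attribution only if their difference were reported, which is not stated. The same edit is needed on either reading.

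Second, Self-Directed is not the absence of a program. The Interventions section describes enhanced usual care with a Fitbit, monthly tip sheets, website access and quarterly calls. A reader might therefore infer that the net figure is the gain over doing nothing. It is not, and it may understate the gain over ordinary care. The documents give no remission rate for ordinary care; the 11.1% in the Background comes from another trial's lifestyle arm. This stands, and it governs how the result must be labelled. The between-arm difference is still the only randomized contrast available, and it matches the ICER.

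Third, three stronger readings are tempting and should not be made.

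- **Run-in selection causes the over-crediting.** It does not. Selection concerns whether the effect carries over to other populations, and it remains a question after the comparator is subtracted.
- **Chance fluctuation around the component thresholds adds a further error.** Such remission occurs in both arms and is already inside the Self-Directed rate. Its size cannot be derived from the documents.
- **The overstatement grows in inverse proportion to the share of people who resemble the trial sample.** That assumes no benefit at all in everyone else and full uptake in the projection. The protocol states neither.

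**Conclusion.** The point holds as a defect of specification with a material consequence on its natural reading. The input to the dissemination model is worded as a level, it disagrees with the incremental effect in the ICER, and the Analysis Plan covers one program where Aim 3b covers two. If the Group-Based rate is used gross, the projected benefit is 2.0 times the gain over Self-Directed at the planning rates, 1.6 times at 15% Self-Directed remission and 1.33 times at 10%, and it is positive even when the arms are equal. These factors assume a Group-Based rate of 40%, and they measure overstatement relative to enhanced usual care only.

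The transportability point is separate and lesser. The sample is highly motivated and run-in selected, while the planned economic sensitivity analyses address cost assumptions alone. The documents do not allow the size of this effect to be computed.

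The projection belongs to a secondary aim. The primary comparison and the ICER do not depend on it.

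**What to change.** 1. In the dissemination paragraph of the Analysis Plan, replace the observed-rate phrase with: *the between-arm difference in 24-month MetS remission (Group-Based minus Self-Directed), with its cluster-adjusted 95% CI carried through the model*. Alternatively, project each arm separately and report the difference with its interval. That version follows Aim 3b and would bring the two sections into agreement.
2. State that the result is the gain over enhanced usual care, not over no program.
3. As a lesser addition, state the uptake and eligible share assumed for each national population, and vary these and the effect size in sensitivity analyses. The trial's own screening and run-in counts are not a suitable source for the eligible share: they reflect recruitment at five sites with locally tailored methods, not the composition of the national populations.

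**Cost.** Items 1 and 2 are wording changes and need no new trial data. Item 3 needs external figures or openly stated assumptions. The projected savings will be smaller and will carry an interval, and they may understate the gain over ordinary care.
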